Appendix 2: Color Analog Scale (CAS)

Subjects aged 6 to less than 12 years will be evaluated for pain using the CAS at screening; at 4, 8, 12, 24, 36, 48, 60, 72, and 96 hours after the end of study drug administration; immediately prior to each administration of postoperative opioid pain management medication till 96 hours; and at hospital discharge. If a subject is too anesthetized at the time of a scheduled pain intensity assessment, the assessment should be skipped.

Using the color scale of 0 to 10 below, where 0 (green color) means no pain and 10 (red color) means worst possible pain, circle the number that best describes how much pain are you having right now? (Circle one number only.)

Appendix 3: Neurological Assessment

The neurological assessment will be conducted at screening; at 2, 4, 8, 12, 24, 48, 60, 72, and 96 hours; at hospital discharge; and on Day 30.

The examination will include the subject's orientation.

Is the subject oriented?
 Yes No Not Assessable

If the subject is not oriented, the event should be recorded as an AE.

Additionally, the subject will be asked the following questions:

- Since your last assessment have you had numbress of the lips, the tongue, or around the mouth?
 Yes
 No
- Since your last assessment have you had a metallic taste in your mouth?

 \Box Yes \Box No

- Since your last assessment, have you had problems with your hearing not related to the use of a hearing aid?
 Yes
 No
- Since your last assessment, have you had problems with your vision not related to the use of eye glasses?
 Yes
 No
- Since your last assessment, have your muscles been twitching?

 \Box Yes \Box No

If the subject answers "yes" to any of these questions, the event should be recorded as an AE and additional safety procedures should be conducted (see Section 13.1.7).

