12.3. Safety Assessments

The following safety measurements will be conducted at the time points specified:

• Vital signs (temperature, resting heart rate, respiratory rate, oxygen saturation, and blood pressure) at screening; upon arrival in the post-anesthesia care unit (PACU); at 2, 4, 8, 12, 24, 36, 48, 60, 72, and 96 hours after the end of study drug administration; at hospital discharge; and on Day 30.

- Neurological assessment at screening; at 2, 4, 8, 12, 24, 36, 48, 60, 72, and 96 hours after the end of study drug administration; at hospital discharge; and on Day 30 (Part 1 only, Appendix 3).
- Clinical laboratory tests (hematology, chemistry, and urinalysis) at screening; at baseline (on Day 1 prior to surgery) and at 96 hours after the end of study drug administration (see Appendix 4).
- AEs from the time the ICF is signed/assent is obtained till Day 30.

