13.1.2. Neurological Examination

A neurological assessment will be conducted during Part 1 only at the following time points: at screening; at 2, 4, 8, 12, 24, 36, 48, 60, 72, and 96 hours after the end of study drug administration; at hospital discharge; and on Day 30. The examination will include the subject's orientation. Additionally, subjects aged 6 years or older will be asked whether he or she is experiencing any numbress of the lips, the tongue, or around the mouth; hearing problems; or muscle twitching (see Appendix 3). If the subject answers "yes" to any of these questions, the event should be recorded as an AE and additional safety procedures should be conducted as appropriate (see Section 13.1.7).

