13.3. Baseline Procedures (Day 1 Prior to Surgery)

- Confirm eligibility.
- Update relevant medical and surgical history.
- Conduct urine pregnancy test for females of childbearing potential. A negative pregnancy test result must be available before surgery.
- Measure vital signs (temperature, resting heart rate, respiratory rate, oxygen saturation, and blood pressure) after subject has rested in a supine position.

- Conduct 12-lead ECG after subject has rested in a supine position.
- Conduct clinical laboratory tests (hematology, chemistry, and urinalysis; Appendix 4).
- Conduct a urine drug screen and alcohol breath test at the investigator's discretion (Part 1 only). Subjects with a positive result will be excluded from the study.
- Record changes to concomitant medications since screening.
- Record AEs and any treatment(s) for the events.

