6.8.3 Neurological Assessments

Neurological assessments include orientation (orientated, disoriented, not assessable), numbness (of lips, tongue, or around mouth), metallic taste, hearing problems, vision problems, and muscle twitching. The number and percentage of subjects will be tabulated for each neurological assessment by treatment group for Group 1 and by surgery type for Group 2, at any time after baseline and at each assessment timepoint.

Time windows will be derived for each post baseline visit using the time intervals for the study time windows detailed in Table 4.

Study Time	Time Interval for Study Time Window
Baseline	≥ 0 minutes prior to dose
Post-dose 2 hours	1.75 – 2.25 hours after end of study drug administration
Post-dose 4 hours	3.75 – 4.25 hours after end of study drug administration
Post-dose 8 hours	7.5 – 8.5 hours after end of study drug administration
Post-dose 12 hours	11 – 13 hours after end of study drug administration
Post-dose 24 hours	23 – 25 hours after end of study drug administration
Post-dose 36 hours	34 – 38 hours after end of study drug administration
Post-dose 48 hours	46 – 50 hours after end of study drug administration
Post-dose 60 hours	58 – 62 hours after end of study drug administration
Post-dose 72 hours	70 – 74 hours after end of study drug administration
Post-dose 96 hours	92 – 100 hours after end of study drug administration
Day 30	27 – 33 days after end of study drug administration

Table 4Analysis Study Time Windows for Neurological Assessments

If there are multiple neurological assessment values for the same parameter prior to the end of study drug administration, the last value will be chosen for Baseline. If there are multiple neurological assessment values in a post-end of study drug administration window, the value closest to the target time point will be chosen for analysis. Unscheduled visits can be mapped to a study time only if the scheduled assessment for that time was not done and an unscheduled visit falls into the time interval for the visit window. Data from both scheduled and unscheduled visits will be listed.

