TREATMENT: treatment-name Assessment Question Schedule Actual Deviation (hrs) (hrs) 5 Site Subject Date and Time (hrs) 1 2 3 4 6 ddmmmyyyyThh:mm Screening _ _ Х Х XXX YYYY Х Х Х Х ddmmmvvvvThh:mm 2 Х Х Х Х XXX.XX XXX NA Х 4 ddmmmvvvvThh:mm Х Х Х XXX.XX XXX Х Х Х ddmmmvvvvThh:mm 8 Х Х Х Х Х Х XXX.XX XXX ddmmmyyyyThh:mm 12 Х Х XXX.XX XXX NA Х Х Х ddmmmyyyyThh:mm 24 Х XXX.XX XXX Х Х Х Х Х ddmmmyyyyThh:mm 36 Х Х Х Х XXX.XX XXX Х Х ddmmmyyyyThh:mm 48 XXX.XX XXX Х Х Х Х Х Х ddmmmyyyyThh:mm 60 Х Х Х Х Х XXX.XX XXX Х ddmmmyyyyThh:mm 72 Х Х Х Х Х Х XXX.XX XXX ddmmmvvvvThh:mm 96 XXX.XX Х Х Х Х Х Х XXX Hospital ddmmmvvvvThh:mm Discharge _ Х Х Х Х Х Х XXX.XX ddmmmvvvvThh:mm Day 30 XXX.XX Х Х Х Х Х Х XXX

*=out of window; NA=Not Assessable

Is subject oriented?
 Do you have numbress of the lips, the tongue or around the mouth?
 Do you have a metallic taste in your mouth?
 Are you having problems with your hearing not related to the use of a hearing aid?
 Are your having problems with your vision not related to the use of eye glasses?
 Are your muscles twitching?
 Source: list SAS datasets used to create table
 SAS X.Y

Note to programmer: Sort by date and time within subject. An asterisk (*) will be placed next to the deviation if an assessment is out of window. See Table of Time and Events for windows. Use this template also for listing:

Listing 16.2-16.1.2: Neurological Assessment (Group 2: 6 to < 12 years) - All Subjects

(Page X of Y)

Protocol: 402-C-319

Listing 16.2-17.1.1.1: All Adverse Events (Group 1: 12 to <17 years) - All Subjects

Treat	ment: trea	atment-	name	
Site	Subject	TEAE	Data Type	Data
XXX	УУУУ	N	Start (Day)	ddmmmyyyyThh:mm (XX)
			Stop (Day)	ddmmmyyyyThh:mm (XX)
			AE Number	X
			System Organ Class	XXXXXXXXXXXXXXXXX
		Preferred	*****	
		Verbatim	XXXXXXXXXXXXXXXXXXXXXXXXXXXXXXXXXXXXXXX	
			Severity	XXXXXXX
			Relationship to Study	XXXXXXX
			Drug	
			Action Taken	*****
			Outcome	XXXXXXXXXXXXX
			Serious	XXX
			Serious Cause(s)	XXXXXXXXXXXXX
				XXXXXXXXXXXXXXXXXXXXXXXXXXXXXXXXXXXXXXX

TEAE: Treatment-emergent AE (Y=TEAE/N=Not TEAE)

Source: list SAS datasets used to create listing SAS X.Y

ddmmmyyyyThh:mm

program name

Note to programmer: If AE is ongoing, put ONGOING in stop row. Do not split an AE across pages. Insert a page break between subjects. Use this template also for listings:

Listing 16.2-17.1.1.2: All Adverse Events (Group 2: 6 to < 12 years) - All Subjects

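### As Appendix 3 words them, the 2 h neurological questions can reach back to screening, whereas Section 13.1.2 and the SAP ask only about the present; one wording anchored to study drug is needed

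*Protocol*

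**What the plan says.** **Question wording.** Protocol Appendix 3 gives the verbatim questionnaire. All five symptom items (perioral numbness, metallic taste, hearing, vision, muscle twitching) refer back to the previous assessment, as in "Since your last assessment have you had a metallic taste in your mouth". A yes is to be recorded as an adverse event and leads to the procedures in Section 13.1.7. The orientation item has no recall period.

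Protocol Section 13.1.2 describes the same examination in the present tense: the child "will be asked whether he or she is experiencing any" of the listed symptoms. It lists three (numbness, hearing, twitching) and leaves out metallic taste and vision. The footnote to SAP Listing 16.2-16.1.1 also uses the present tense: "Do you have a metallic taste in your mouth".

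**Schedule.** Protocol Section 12.3 specifies: "Neurological assessment at screening; at 2, 4, 8, 12, 24, 36, 48, 60, 72, and 96 hours". Appendix 3 has the same sequence at the start: "The neurological assessment will be conducted at screening; at 2, 4, 8, 12, 24, 48, 60, 72, and 96 hours". (It omits 36 h, a separate discrepancy that does not bear on this point.) Table 1, Section 13.1.2 and SAP Section 9 agree that nothing comes between screening and 2 h. The Day 1 pre-surgery list in Section 13.3 repeats vital signs and laboratory tests but has no neurological assessment. Screening may be up to 30 days before study drug (Section 9.1).

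**Analysis.** Section 12.4 makes the proportion of subjects with any neurologic event a safety endpoint. SAP Section 6.8.3 tabulates each item "at any time after baseline and at each assessment timepoint", with no condition on when the symptom began. Section 13.1.2 limits the assessment to Part 1.

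**The concern.** The 2 h assessment is the first look at the child after dosing. Under the Appendix 3 wording its recall period opens at screening, so the answer mixes time before dosing with time after it. At screening the question has no earlier assessment to refer to, yet the SAP takes the last pre-dose value, normally the screening one, as Baseline.

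The present-tense wording has the opposite weakness. Protocol Section 7.3 places the first concentration peak at roughly 0 to 2 hours, and no neurological assessment is scheduled before 2 h. A symptom that appears and resolves in that interval is not picked up by the questionnaire.

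The two wordings therefore measure different things, and the documents allow both to feed the same table rows. What is at stake is the reading of a stated safety summary at its first post-dose time point. In the single-arm younger group no comparator is asked the same question.

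**Working it through.** There is no stated figure to reproduce: Section 15.1 rules out hypothesis testing, and no rate is given for these items. The check is of the schedule, followed by simple arithmetic.

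**1. Recall period at 2 h under the Appendix 3 wording.** Inputs: the latest prior neurological assessment is screening, *d* days before dosing, with *d* up to 30; the 2 h assessment is timed from the end of administration. Ignoring the time taken to administer the drug, recall = 24*d* + 2 hours and post-dose share = 2 / (24*d* + 2).

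| Screening to dose | Recall at 2 h | Post-dose share |
|---|---|---|
| 1 day | 24 + 2 = 26 h | 2/26 = 7.7% |
| 7 days | 168 + 2 = 170 h | 2/170 = 1.2% |
| 14 days | 336 + 2 = 338 h | 2/338 = 0.6% |
| 30 days | 720 + 2 = 722 h | 2/722 = 0.28% |

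These are shares of elapsed time, not probabilities that a yes is wrongly placed.

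**2. Where a carried-over yes ends up.**

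- *Neurological tables (SAP Section 6.8.3, Tables 14.3-2.1.x):* counted at 2 h and at any time after baseline, whatever the onset.
- *Adverse event tables:* onset date and time are recorded (Protocol Section 14.1.2). Onset before study drug makes the event pre-treatment (Section 14.1.1), and SAP Section 6.8.4 summarizes only treatment-emergent events. A known pre-dose onset stays out.
- *Incomplete onset:* SAP Section 6.1.1.3 imputes a missing start time on the dosing date to the end of administration, and a missing start day in the dosing month to the dosing day. Such an event can become treatment-emergent. SAP Section 6.8.4 also mentions the stop date, so a recorded stop before dosing may still keep it out.

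**3. What each wording captures at 2 h.**

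| Symptom | Appendix 3 | Section 13.1.2 / SAP listing |
|---|---|---|
| Resolved before dosing | Yes (carried over) | No |
| Arose and resolved between dosing and 2 h | Yes | No |
| Present at 2 h | Yes | Yes |

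**4. Illustration only.** Let *p* be an assumed probability that a child had any of the five symptoms between screening and dosing and would report it at 2 h. For one arm of 15, P(at least one carried-over yes) = 1 − (1 − *p*)^15.

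- *p* = 1%: 1 − 0.99^15 = 14%; expected 0.15 children
- *p* = 5%: 1 − 0.95^15 = 54%; expected 0.75
- *p* = 10%: 1 − 0.90^15 = 79%; expected 1.5

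The values of *p* have no source in the documents. The any-of-five count matches the Section 12.4 endpoint, but the SAP mock-up shows each question on its own row, with no combined row.

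**The case against.** **The CRF may already use the present tense.** The SAP lists CRF version 4.0 (17 March 2019), later than the protocol (1 October 2018), among the documents it was prepared from, and its own footnotes are in the present tense. The CRF is not available here. This stands: the carry-over depends on sites following Appendix 3. The conflict between the documents remains either way.

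**The previous assessment need not mean the previous neurological one.** The child also has Day 1 pre-operative assessments and vital signs on PACU arrival. On that reading the recall period is much shorter. This stands as an ambiguity, and it is a further reason to name the anchor.

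**A reader might infer that pre-dose symptoms will inflate treatment-emergent or special-interest event rates.** The documents do not support that. Those tables go by onset, and adverse events are collected from consent and again on Day 1 before surgery, so a symptom in that interval has its own dated route of capture. Only incomplete onset leaves a gap.

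**A reader might also infer that present-tense wording loses early events altogether.** It does not. Adverse event recording runs to Day 30 independently of the questionnaire, so a resolved early symptom can still be reported. What is lost is its systematic elicitation.

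**Both randomized arms are asked the same questions.** In Group 1, carry-over should not differ systematically between arms. That is correct. It would still raise the level in each arm, and Group 2 has no comparator.

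**Conclusion.** The point holds in a conditional and limited form. If the Appendix 3 wording is used and taken to mean the last neurological assessment, a symptom that resolved before dosing can enter the Part 1 neurological summary as a post-baseline finding, at 2 h and in the count at any time after baseline. If the Section 13.1.2 and SAP wording is used, that does not happen, but the questionnaire cannot register a symptom that resolves before 2 h. The documents do not say which wording applies, so the meaning of the 2 h row is not settled.

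The number of subjects affected cannot be stated. The 14% to 79% range follows wholly from assumed rates and should not be read as an estimate. Beyond the 2 h and cumulative entries, the orientation item, Part 2 and the later time points are unaffected, provided the 2 h assessment is done. It is a modest defect in a descriptive safety endpoint, and worth correcting because the remedy is so small.

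**What to change.** In Appendix 3, use three anchors:

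- at screening, ask whether the child has the symptom now;
- at 2 h, ask about any time since the study drug was given (if the 2 h assessment is missed, use this anchor at the first post-dose assessment actually done);
- from 4 h on, keep the look-back to the last assessment, stating that this means the last neurological assessment.

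Align Section 13.1.2, the CRF and the SAP listing footnotes to this wording, with the same five symptoms in each. The recall period at 2 h then falls from as much as 722 h to about 2 h, carry-over is removed by design, and symptoms in the first two hours are elicited.

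Optionally, add to SAP Section 6.8.3 that a yes which can be matched to its recorded adverse event is not counted as post-baseline when that event began before the start of study drug. This is secondary: onset is already collected, but the documents describe no link from questionnaire item to event, so the matching would have to be specified.

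The cost is a CRF wording update, matching edits to the protocol and SAP, and notice to sites. No visit, assessment or subject is added. If some children have already been assessed, record which wording each was asked so that the 2 h results can be read accordingly.

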Appendix 4: Clinical Laboratory Tests

The scheduled clinical laboratory tests (hematology, chemistry, and urinalysis) will be conducted at screening; at baseline (on Day 1 prior to surgery); and at 96 hours.

Additionally, appropriate clinical laboratory tests should be conducted if a subject experiences a cardiac or neurological AE of special interest or an SAE (see Section 13.1.7).

[figure not shown]
General Chemistry Analysis	General Hematology (CBC with Differential) Components	Urinalysis
Albumin	White blood cells	Color
Alkaline phosphatase	Red blood cells	Appearance
Alanine transaminase (ALT)	Hemoglobin	Specific gravity
Amylase	Hematocrit	рН
Aspartate transaminase (AST)	Mean corpuscular volume	Protein
Bilirubin, direct	Mean corpuscular hemoglobin	Glucose
Bilirubin, total	Mean corpuscular hemoglobin	Ketones
Blood urea nitrogen	concentration	Bilirubin
Calcium	Red cell distribution width	Blood
Carbon dioxide (bicarbonate)	Platelets	Urobilinogen
Chloride	Mean platelet volume	Nitrite
Cholesterol	Absolute/percent neutrophil count	Leukocyte esterase
Creatine kinase (CK), total (or creatine phosphokinase [CPK])	Absolute/percent lymphocyte count Absolute/percent monocyte count	
Creatinine, serum	Absolute/percent eosinophil count	
Gamma-glutamyl transpeptidase (GGT)	Absolute/percent basophil count	
Glucose		
Iron		
Unsaturated/Total Iron binding capacity (UIBC/TIBC)		
Lactate dehydrogenase (LDH)		
Lipase		
Magnesium		
Phosphorus		
Potassium		
Sodium		
Total protein		
Transferrin		
Triglycerides		
Uric acid		

Age (years)	Males	Females
2	14.7 – 19.3	14.4 - 19.1
3	14.3 - 18.2	14.0 - 18.3
4	14.0 - 17.8	13.7 - 18.0
5	13.8 - 18.0	13.5 - 18.2
6	13.8 - 18.4	13.4 - 18.8
7	13.7 - 19.2	13.4 - 19.6
8	13.8 - 20.0	13.5 - 20.7
9	14.0 - 21.0	13.8 - 21.8
10	14.2 - 22.1	14.0 - 22.9
11	14.5 - 23.2	14.4 - 24.1
12	15.0 - 24.2	14.8 - 25.2
13	15.4 - 25.2	15.3 - 26.2
14	16.0 - 26.0	15.8 - 27.2
15	16.5 - 26.8	16.3 - 28.1
16	17.1 - 27.6	16.8 - 28.9

Appendix 5:BMI Normal Ranges (5th to 95th Percentile)

Adapted from: Centers for Disease Control and Prevention, National Center for Health Statistics, http://www.cdc.gov/growthcharts/clinical_charts.htm

Periodic DSMB review of all events (AESI, SAE, AE)

1. INTRODUCTION

This Statistical Analysis Plan (SAP) describes the planned statistical analyses and reporting of the clinical study 402-C-319 titled "A Multicenter Study to Evaluate the Pharmacokinetics and Safety of EXPAREL[®] for Postsurgical Analgesia in Pediatric Subjects Aged 6 to Less Than 17 Years".

The structure and content of this SAP provide sufficient detail to meet the requirements identified by the US Food and Drug Administration (FDA), European Medicines Agency (EMA), and International Conference on Harmonisation (ICH) of Technical Requirements for Registration of Pharmaceuticals for Human Use: Guidance on Statistical Principles in Clinical Trials.¹ All work planned and reported for this SAP will follow internationally accepted statistical practice guidelines, published by the American Statistical Association² and the Royal Statistical Society³.

The purposes of this SAP are to:

- Outline the analyses and presentations of data that will form the basis for drawing conclusions regarding the study objectives and hypotheses outlined in the protocol.
- Explain how the data will be handled and analyzed, adhering to commonly accepted standards and practices for Good Statistical Practice.

The planned analyses identified in this SAP may be included in clinical study reports (CSRs), regulatory submissions, or manuscripts. Post-hoc exploratory analyses not necessarily identified in this SAP may be performed to further examine study data. Any post-hoc, unplanned, or exploratory analyses performed will be clearly identified as such in the final CSR.

The following documents were reviewed in preparation of this SAP:

- Original Protocol 402-C-319 issued on 01Oct2018.
- CRF version 4.0 issued on 17Mar2019.
- ICH Guidance on Statistical Principles for Clinical Trials (E9)

The reader of this SAP is encouraged to also read the clinical protocol and other identified documents for details on the planned conduct of this study. Operational aspects related to collection and timing of planned clinical assessments are not repeated in this SAP unless relevant to the planned analyses.

2. STUDY OBJECTIVES

2.1 Primary Objective

The primary objective is to evaluate the pharmacokinetics (PK) of EXPAREL in pediatric subjects aged 6 to less than 17 years undergoing various types of surgeries.

2.2 Secondary Objective

The secondary objective is to evaluate the safety of EXPAREL in pediatric subjects aged 6 to less than 17 years undergoing various types of surgeries.

3. STUDY OVERVIEW

This is a two-part study to evaluate the PK and safety of EXPAREL in pediatric subjects aged 6 to less than 17 years. Part 1 will evaluate the PK and safety in subjects aged 6 to less than 17 years, while Part 2 will assess the safety in subjects aged 6 to less than 17 years. This is also a two-group study. Group 1 will include subjects aged from 12 to <17 years old undergoing spine surgery. Group 2 will include subjects aged from 6 to <12 years old undergoing spine or cardiac surgery. (Table 1)

In Part 1, subject enrollment will be conducted in parallel to include the older age group (12 to <17 years old; Group 1) and the younger age group (6 to <12 years old; Group 2).

Subject enrollment for Part 2 (of each group) will commence upon completion of Part 1 (of that group). In Part 2, subject enrollment will be conducted in parallel to include the older age group (12 to <17 years old; Group 1) and the younger age group (6 to <12 years old; Group 2).

Dosing of EXPAREL will be based on body weight, with a starting dose of 4 mg/kg (maximum 266 mg). Dosing of Bupivacaine HCl will be based on body weight, with a starting dose of 2 mg/kg (maximum 175 mg).

	Part 1 (PK and Safety)	Part 2 (Safety)
Group 1: subjects aged 12 to <17 years	EXPAREL 4 mg/kg [N=15]; or	EXPAREL 4 mg/kg [N = 15]; or
(Surgery: Spine Surgery)	bupivacaine HCl 2 mg/kg [N =15]	bupivacaine HCl 2 mg/kg [N =15]
Group 2: subjects aged 6 to <12 years (Surgery: Spine or Cardiac Surgery)	EXPAREL 4 mg/kg [N=15]	EXPAREL 4 mg/kg [N =15]

Part 1 (Pharmacokinetics [PK]) - Subjects aged 6 to less than 17 years

Part 1 is a multicenter, randomized, open-label study in 45 subjects aged 6 to less than 17 years of age undergoing spine or cardiac surgeries. Part 1 is divided in 2 groups: Group 1 will include subjects aged 12 to less than 17 years of age, while Group 2 will include subjects aged 6 to less than 12 years of age.

Part 1, Group 1, is an active-controlled, open-labeled, PK evaluation study in subjects aged 12 to less than 17 years undergoing spine surgery. The active comparator will be bupivacaine HCl. The planned sample size for Part 1, Group 1 is 30 subjects (15 subjects per treatment group). Subjects will be randomized 1:1 to receive either a single dose of EXPAREL 4 mg/kg (maximum 266 mg) or bupivacaine HCl 2 mg/kg (not exceeding a maximum bupivacaine HCl dose of 175 mg total) intraoperatively at the end of surgery via local infiltration.

Part 1, Group 2, is a single arm (EXPAREL 4 mg/kg), open-label, PK evaluation study in subjects aged 6 to less than 12 years undergoing spine or cardiac surgery. The planned sample size for Part 1 Group 2 is 15 subjects. Subjects will receive a single dose of EXPAREL 4 mg/kg (maximum 266 mg) intraoperatively at the end of surgery via local infiltration.

Part 2 (Safety) - Subjects aged 6 to less than 17 years

Part 2 is a multicenter, randomized, open-label study in 45 subjects aged 6 to less than 17 years of age undergoing spine or cardiac surgeries. Part 2 is divided in 2 groups: Group 1 will include subjects aged 12 to less than 17 years of age, while Group 2 will include subjects aged 6 to less than 12 years of age.

Part 2, Group 1, is an active-controlled, open-labeled, safety evaluation study in subjects aged 12 to less than 17 years undergoing spine surgery. The active comparator will be bupivacaine HCl. The planned sample size is 30 subjects (15 subjects per treatment group) for Part 2 Group 1. Subjects will be randomized 1:1 to receive either a single dose of EXPAREL 4 mg/kg (maximum 266 mg) or bupivacaine HCl 2 mg/kg (not exceeding a maximum bupivacaine HCl dose of 175 mg total) intraoperatively at the end of surgery via local infiltration.

Part 2, Group 2, is a single arm (EXPAREL 4 mg/kg), open-label study in subjects aged 6 to less than 12 years undergoing spine or cardiac surgery. The planned sample size for Part 2 Group 2 is 15 subjects. Subjects will receive a single dose of EXPAREL 4 mg/kg (maximum 266 mg) intraoperatively at the end of surgery via local infiltration.

Screening Procedures

Subjects will be screened within 30 days prior to study drug administration. During the screening visit, subjects will be assessed for past or present neurologic, cardiac, and general medical conditions that, in

the opinion of the investigator, would preclude them from study participation. After the Informed Consent Form (ICF) is signed by the subject's legal guardian and written assent is provided by the subject (if capable), medical history, surgical history, physical examination, 12-lead electrocardiogram (ECG), vital sign measurements, neurological assessment, clinical laboratory tests (hematology, chemistry, and urinalysis), pain intensity score assessment, urine pregnancy test (for females of childbearing potential), urine drug screen and alcohol breath test will be conducted.

Study Procedures

On Day 1, eligible subjects will receive the study drug intraoperatively at the end of surgery via local infiltration to produce analgesia. Use of intraoperative opioids, acetaminophen, ketorolac, or other NSAIDs, will be permitted in accordance with the study site's standard of care.

Avoid additional use of local anesthetics within 96 hours following the administration EXPAREL.

There is no required length of stay in the hospital; subjects may be discharged based on the medical judgement of the treating physician. For subjects discharged from the hospital before all protocol-specified assessments until 96 hours are completed, a nurse will perform follow-up visits at the subject's home to perform the required postsurgical assessments and collect PK samples until 96 hours.

A follow-up phone call will be scheduled for all subjects on Day 7. For the assessment of AEs, a final follow-up visit will be made on Day 30 to all subjects who would have received the study drug.

Postsurgical Pain Management

Use of postsurgical pain medication in cases of insufficient analgesia will be permitted according to the institution's standard of care. The investigator must record all postsurgical pain management medications provided to the subjects until the hospital discharge.

Avoid additional use of local anesthetics within 96 hours following the administration EXPAREL.

Postsurgical Assessments

Postsurgical assessments to be conducted until 96 hours include pain intensity using 11-point Numerical Rating Scale at Rest (NRS-R) for subjects aged 12 to less than 17 years and the Color Analog Scale (CAS) for subjects age 6 to less than 12 years; neurological assessment, clinical laboratory tests, and vital signs.

AEs will be recorded from the time of ICF is signed/assent is given until Day 30.

The study protocol specified that if a cardiac or neurological AE of special interest (AESI) or serious AE (SAE) occurs during the study, if the investigator or medical monitor considers that the event may be related to study treatment or suggests the possible occurrence of local anesthetic systemic toxicity (LAST; with or without the need for treatment [e.g., intralipids]), or if a plausible etiology for the event cannot be found, an unscheduled PK blood sample must be collected and a 12-lead ECG, vital signs, and clinical laboratory tests (hematology and complete metabolic profile [CMP]) according to the study site's standard of care may be conducted. Cardiac and neurological AEs that do not meet one of these three criteria for AESI should be reported and captured in the database as an AE.

Cardiac AESIs include chest pain, abnormal/irregular heart rate, and shortness of breath requiring intervention. Neurologic AESIs include seizure, altered mental status/altered sensorium, rigidity, dysarthria, tremors, tinnitus, visual disturbance, and severe or worsening dizziness (see below). Additionally, the following events may be of special interest if they persist or occur beyond 72 hours post dose: dizziness, hyperesthesia, muscular twitching, and tingling/paresthesia.

Dizziness will be assessed as mild, moderate, or severe based on the National Cancer Institute-Common Terminology Criteria for Adverse Events (NCI-CTCAE) Version 5.0. Mild dizziness is defined as mild

unsteadiness or sensation of movement; moderate dizziness is defined as moderate unsteadiness or sensation of movement limiting instrumental activities of daily living (ADL); and severe dizziness is defined as severe unsteadiness or sensation of movement that limits self-care ADLs. Dizziness will be captured as an AESI if it is severe or worsens or persist beyond 72 hours post dose.

4. **DEFINITIONS**

Study Day

If the date of the event is on or after the date of the end of study drug administration, Study Day is calculated as the date of the event minus the date of the end of study drug administration plus one (1). If the date of the event is before the date of the end of study drug administration, Study Day is the date of the event minus the date of the end of study drug administration.

Treatment-emergent Adverse Events

Treatment-emergent adverse events (TEAEs) are those with onset on or after the start time of study drug administration, and before or at the end of the study (expected to be Study Day 30 ± 3 days).

Time 0 (zero)

Time 0 is defined as the time of the end of study drug administration, with the exception of AE's and concomitant medications. Time 0 for AE's and concomitant medications are defined as the time of the start of study drug administration.

Time Deviation

For PK sampling time window, *Time Deviation* is the difference (actual – start/end of target window of assessment) between the actual and target window of assessment in the PK sampling. If sampling occurred before the beginning of target window of assessment, time deviation will be calculated by subtracting the actual time from the beginning of the target window of assessment. If the sampling occurred after the end of target window of assessment, time deviation will be calculated by subtracting the actual sampling time from the end of the target window of assessment. Any samples occurring with the target window will have a time deviation of 0.

Baseline

Baseline measurement or assessment is defined as the last available measurement or assessment prior to the start of study drug administration.

Last Follow-up Time

For subjects who withdraw prematurely, the last follow-up time will be defined as the maximum of the last pain or any other study assessment, the last concomitant medication start or end datetime, and the last adverse event start or end datetime.

